#### COVID-19 Pandemic-Related Acceptable Protocol Modification

During the COVID 19 pandemic, it has been necessary to employ mitigation strategies to enable the investigator to ensure subject safety and continuity of care. Acceptable mitigation strategies are identified and included in the Operations Manual in [Appendix F](#).

The investigator should contact the sponsor medical contact before discontinuing a subject from the study for a reason other than "planned per protocol," to ensure all acceptable mitigation steps have been explored.

Refer to the Operations Manual in [Appendix F](#) for details on how to handle study activities/procedures.

#### Interruption/Discontinuation of Study Drug Due to COVID-19 Infection

For subjects with documented COVID-19, the timing of next administration of study drug or possibility of premature discontinuation from study drug should be discussed with the AbbVie Medical Contact. Follow subsequent protocol Section [5.6](#) for subjects who discontinued study drug.

## 5.6 Follow-Up for Subject Withdrawal from Study

---

To minimize missing data for efficacy and safety assessments, subjects who prematurely discontinue study drug treatment should continue to be followed for all regularly scheduled visits, unless subjects have decided to discontinue the study participation entirely (withdrawal of informed consent). Subjects should be advised on the continued scientific importance of their data even if they discontinue treatment with study drug early.

If a subject prematurely discontinues study participation, the procedures outlined for the Premature Discontinuation visit should be completed as soon as possible, preferably within 2 weeks. In addition, if subject is willing and has not withdrawn consent, a 20-week follow-up phone call after the last dose of study drug may be completed to ensure all treatment-emergent AEs/SAEs have been resolved.

In the event a subject withdraws consent from the clinical study, biomarker research will continue unless the subject explicitly requests analysis to be stopped. When AbbVie is informed that samples are withdrawn from research, samples will not be analyzed, and the samples will be destroyed. A subject may withdraw consent for optional biomarker research at any time and remain in the clinical study. Data generated from optional biomarker research, before subject withdrawal of consent, will remain part of the study results.

## 5.7 Study Drug

Information about the study drug and placebo used in this study is presented in (Table 1).

**Table 1. Identity of Investigational Product**

Study Drug	Dosage Form	Formulation	Route of Administration	Manufacturer
Risankizumab (ABBV-066)	Solution for injection in pre-filled syringe (PFS)	90 mg/mL	SC injection	Boehringer-Ingelheim Pharma GmbH & Co. KG
Placebo for risankizumab (ABBV-066)	Solution for injection in PFS	N/A	SC injection	Boehringer-Ingelheim Pharma GmbH & Co. KG

N/A = not applicable; PFS = pre-filled syringe; SC = subcutaneous

Through Week 12 of Period A, study site staff will administer study drug subcutaneously as follows:

- Risankizumab 180 mg (2 × 90 mg PFS and 2 × placebo PFS)
- Risankizumab 360 mg (4 × 90 mg PFS), or
- Matching placebo (4 × placebo PFS).

At Weeks 16, 17, and 18 in Period B, subjects who were originally randomized to receive risankizumab 180 mg or 360 mg in Period A will receive placebo. Subjects who were originally randomized to receive placebo will receive risankizumab 360 mg.

Beginning with Week 20 in Period B, study site staff will administer open-label risankizumab 360 mg subcutaneously as described above q8w until the end of the study.

Risankizumab and matching placebo will be packaged in quantities sufficient to accommodate study design. Each kit will be labeled per local requirements, and this label must remain affixed to the kit. Upon receipt, study drug should be kept in the original packaging in a secured limited access storage area according to the recommended storage conditions on the medication label. No extemporaneous dose preparation is required.

Each kit will contain a unique kit number. This kit number is assigned to a subject via interactive response technology (IRT) and encodes the appropriate study drug to be dispensed at the subject's corresponding study visit.

AbbVie will not supply drug other than risankizumab and matching placebo, and study drug will only be used for the conduct of this study. AbbVie-provided study drug should not be substituted or alternately sourced unless otherwise directed by AbbVie.

## 5.8 Randomization/Drug Assignment

---

Each subject will be assigned a unique identification number by the IRT at the screening visit. For subjects who rescreen, the screening number assigned by the IRT at the initial screening visit should be used. Subjects may only be rescreened one time. The IRT will assign a randomization number that will encode the subject's treatment group assignment according to the randomization schedule generated by the statistics department at AbbVie.

Subjects who meet the study's eligibility criteria will be initially randomized to receive either risankizumab 180 mg or 360 mg as an SC injection or matching placebo up to Week 16 in a 1:1:1 ratio.

Subjects who have been treated with anti-TNF therapy and had inadequate response to this therapy (TNF- IR) will be eligible. Subjects will be randomized by their anti-TNF use (yes or no) prior to Baseline. TNF-naïve (no) subjects will be further stratified by the worst Hurley stage across all affected anatomic regions. Therefore, there will be 4 strata in total:

- Prior exposure to anti-TNF (yes)
- Prior exposure to anti-TNF (no) with the worst Hurley Stage as I
- Prior exposure to anti-TNF (no) with the worst Hurley Stage as II
- Prior exposure to anti-TNF (no) with the worst Hurley Stage as III

All AbbVie personnel with direct oversight of the conduct and management of the study (with the exception of AbbVie Drug Supply Management Team) will remain blinded until the Primary Analysis at Week 16 is available. The investigator, study site personnel, and the subject will remain blinded to each subject's initial treatment throughout the study. To maintain the blind, the risankizumab kits and placebo kits provided for the study will be identical in appearance. The IRT will provide access to unblinded subject treatment information in the case of a medical emergency.

## 5.9 Protocol Deviations

---

The investigator is responsible for complying with all protocol requirements, written instructions, and applicable laws regarding protocol deviations. Protocol deviations are prohibited except when necessary to eliminate an immediate hazard to study subjects. If a protocol deviation occurs (or is identified, including those that may be due to the COVID-19 pandemic), the investigator is responsible for notifying IEC/IRB, regulatory authorities (as applicable), and AbbVie.

# 6 SAFETY CONSIDERATIONS

## 6.1 Complaints and Adverse Events

---

### Complaints

A complaint is any written, electronic, or oral communication that alleges deficiencies related to the physical characteristics, identity, quality, purity, potency, durability, reliability, safety, effectiveness, or

performance of a product/device. Complaints associated with any component of this investigational product must be reported to AbbVie.

### Product Complaint

A product complaint is any complaint related to the biologic or drug component of the product or to the medical device component(s).

For a product this may include, but is not limited to, damaged/broken product or packaging, product appearance whose color/markings do not match the labeling, labeling discrepancies/inadequacies in the labeling/instructions (e.g., printing illegible), missing components/product, device not working properly, or packaging issues.

Product complaints concerning the investigational product and/or device must be reported to AbbVie within 24 hours of the study site's knowledge of the event. Product complaints occurring during the study will be followed up to a satisfactory conclusion.

### Medical Complaints/Adverse Events and Serious Adverse Events

An AE is defined as any untoward medical occurrence in a subject or clinical investigation subject administered a pharmaceutical product and which does not necessarily have a causal relationship with this treatment. An AE can therefore be any unfavorable and unintended sign (including an abnormal laboratory finding), symptom, or disease temporally associated with the use of a medicinal (investigational) product, whether or not the event is considered causally related to the use of the product.

Such an event can result from use of the drug as stipulated in the protocol or labeling, as well as from "special situations" as accidental or intentional overdose, medication error, occupational or accidental exposure, off-label use, drug abuse, drug misuse or drug withdrawal, all which must be reported whether associated with an adverse event or not. Any worsening of a pre-existing condition or illness is considered an AE. Worsening in severity of a reported AE should be reported as a new AE. Laboratory abnormalities and changes in vital signs are considered to be an AE only if they result in discontinuation from the study, necessitate therapeutic medical intervention, meet protocol-specific criteria, and/or the investigator considers it to be an AE.

The investigators will monitor each subject for clinical and laboratory evidence of AEs on a routine basis throughout the study. All AEs will be followed to a satisfactory conclusion.

An elective surgery/procedure scheduled to occur during a study will not be considered an AE if the surgery/procedure is being performed for a pre-existing condition and/or the surgery/procedure has been pre planned prior to study entry. However, if the pre-existing condition deteriorates unexpectedly during the study (e.g., surgery performed earlier than planned), then the deterioration of the condition for which the elective surgery/procedure is being done will be considered an AE.

If an AE, whether associated with study drug or not, meets any of the following criteria, it is to be reported to AbbVie clinical pharmacovigilance as a SAE within 24 hours of the site being made aware of the SAE (refer to Section 4.3 of the Operations Manual for reporting details and contact information):

Death of Subject	An event that results in the death of a subject.
Life-Threatening	An event that, in the opinion of the investigator, would have resulted in immediate fatality if medical intervention had not been taken. This does not include an event that would have been fatal if it had occurred in a more severe form.
Hospitalization or Prolongation of Hospitalization	An event that results in an admission to the hospital for any length of time or prolongs the subject's hospital stay. This does not include an emergency room visit or admission to an outpatient facility.
Congenital Anomaly	An anomaly detected at or after birth, or any anomaly that results in fetal loss.
Persistent or Significant Disability/Incapacity	An event that results in a condition that substantially interferes with the activities of daily living of a study subject. Disability is not intended to include experiences of relatively minor medical significance such as headache, nausea, vomiting, diarrhea, influenza, and accidental trauma (e.g., sprained ankle).
Important Medical Event Requiring Medical or Surgical Intervention to Prevent Serious Outcome	An important medical event that may not be immediately life-threatening or result in death or hospitalization, but based on medical judgment may jeopardize the subject and may require medical or surgical intervention to prevent any of the outcomes listed above (i.e., death of subject, life threatening, hospitalization, prolongation of hospitalization, congenital anomaly, or persistent or significant disability/incapacity). Additionally, any elective or spontaneous abortion or stillbirth is considered an important medical event. Examples of such events include allergic bronchospasm requiring intensive treatment in an emergency room or at home, blood dyscrasias or convulsions that do not result in inpatient hospitalization, or the development of drug dependency or drug abuse.

All AEs reported from the time of study drug administration until 20 weeks (140 days) after discontinuation of study drug administration will be collected, whether solicited or spontaneously reported by the subject. In addition, SAEs and protocol-related nonserious AEs will be collected from the time the subject signs the study-specific informed consent.

AbbVie will be responsible for Suspected Unexpected Serious Adverse Reactions (SUSAR) reporting for the Investigational Medicinal Product in accordance with global and local requirements.

Adverse events will be monitored throughout the study to identify any of special interest that may indicate a trend or risk to subjects.

## Areas of Safety Interest/Safety Topics of Interest

Subjects will be screened and monitored throughout the study for ASI/Safety Topics of Interest. Screening procedures are outlined in the Activity Schedule ([Appendix D](#)). In consideration of the ASI, the following supplemental eCRFs must be completed if AEs in any of the following areas are reported during the study ([Table 2](#)).

**Table 2. Supplemental Adverse Events eCRFs**

Adverse Event	Supplemental eCRF
Cardiac events Myocardial infarction or unstable angina Cerebral vascular accident Cardiovascular death	
 
Cardiovascular History and CV Risk Factors eCRF
 
Cardiovascular (Cardiac) AE eCRF
 
Myocardial Infarction and Unstable Angina AE eCRF
 
Heart Failure AE eCRF
 
Cerebral Vascular Accident and Transient Ischemic Attack AE eCRF
 
Combination Thrombotic Event AE eCRF
 
Arrhythmia AE eCRF
 

Discontinuation or interruption of study drug due to a Hepatic-related AE Hepatic-related SAE	
 
Hepatic AE eCRF
 

Suspected anaphylactic/systemic hypersensitivity reactions	
 
Hypersensitivity Reaction Signs and Symptoms eCRF
 

TB Subjects will be screened for TB (using the TB Screening Form) and those with active TB will be excluded from participation in the study. Subjects with events of latent TB or suspected active TB after initiation of study drug should have a TB Supplemental Form completed.	
 
TB Screening eCRF
 
TB Supplemental eCRF
 

Death	
 
Death eCRF
 

AE = adverse event; CV = cardiovascular; eCRF = electronic case report form; SAE = serious adverse event; TB = tuberculosis

## Adverse Event Severity and Relationship to Study Drug

Adverse events must be graded to the 5 criteria described in the National Cancer Institute (NCI) Common Terminology Criteria for Adverse Events (CTCAE) Version 5.

If no specific criteria per CTCAE Version 5 guidelines are available for the reported event, the event should be graded per the investigator's judgment:

- Grade 1 (Mild):** Asymptomatic or mild symptoms; clinical or diagnostic observations only; intervention not indicated.

- **Grade 2 (Moderate):** Minimal, local or noninvasive intervention indicated; limiting age-appropriate instrumental activities of daily living.
- **Grade 3 (Severe):** Medically significant but not immediately life-threatening; hospitalization or prolongation of hospitalization indicated; disabling; limiting self-care activities of daily living.
- **Grade 4 (Severe):** Life-threatening consequences; urgent intervention indicated.
- **Grade 5 (Severe):** Death related to AE.

The investigator will use the following definitions to assess the relationship of the AE to the use of study drug:

Reasonable Possibility	After consideration of factors including timing of the event, biologic plausibility, clinical judgment, and potential alternative causes, there is sufficient evidence (information) to suggest a causal relationship.
No Reasonable Possibility	After consideration of factors including timing of the event, biologic plausibility, clinical judgment, and potential alternative causes, there is insufficient evidence (information) to suggest a causal relationship.

## Pregnancy

While not an AE, pregnancy in a study subject must be reported to AbbVie within 24 hours after the site becomes aware of the pregnancy. Subjects who become pregnant during the study must be discontinued (Section 5.5). If a pregnancy occurs in a study subject, information regarding the pregnancy and the outcome will be collected.

The pregnancy outcome of an elective or spontaneous abortion, stillbirth, or congenital anomaly is considered a SAE and must be reported to AbbVie within 24 hours after the site becomes aware of the event.

## 6.2 Independent Data Monitoring Committee

---

An external IDMC will review unblinded safety data on a cohort level, at approximate 6-month intervals throughout the course of the study.

- A separate IDMC charter will be prepared outside of the protocol and will describe the roles and responsibilities of the IDMC members, frequency and triggers of data reviews, and relevant safety data to be assessed. Unblinded adjudicated cardio-cerebrovascular events will be presented to the IDMC for review on a periodic basis.
- Communications from the IDMC to the Study Teams will not contain information that could potentially unblind the team to subject treatment assignments.

## 6.3 Cardiovascular Adjudication Committee

---

An independent adjudication committee will be adjudicating all observed cardio- and cerebro-vascular events and will remain blinded to treatment allocation. The events that are adjudicated and the adjudication process will be detailed in the CAC Charter. Dedicated eCRFs will be used as outlined in [Table 2](#).

In addition, the site may be contacted for additional source documentation for relevant events.

## 6.4 Anaphylaxis Adjudication Committee

---

While no concerns with systemic hypersensitivity have been identified with the use of risankizumab, the sponsor has established the AAC to adjudicate events of anaphylaxis based on pre-specified definitions. This independent, external committee will adjudicate suspected anaphylactic reactions and will remain blinded to treatment allocation. The event terms to be adjudicated and the adjudication process are detailed in the AAC Charter. A supplemental Hypersensitivity Reactions Signs and Symptoms eCRF will be used to collect information pertinent to the events ([Table 2](#)). In addition, the site may be contacted for additional source documentation for relevant events.

If a suspected systemic hypersensitivity reaction occurs at the investigative site, subjects should be tested for tryptase and histamine levels. In addition to testing tryptase and histamine levels, pharmacokinetic (PK) and ADA/NAb samples will also be collected. If a systemic hypersensitivity reaction such as anaphylaxis is suspected while the subject is not at the investigative site, every effort should be made to obtain tryptase and histamine levels from the treating facility to help better characterize the diagnosis.

# 7 STATISTICAL METHODS & DETERMINATION OF SAMPLE SIZE

## 7.1 Statistical and Analytical Plans

---

The Primary Analysis will be conducted after all continuing subjects complete Week 16 and all data pertaining to Period A are cleaned. This will be the only and final analysis for efficacy in Period A. Study sites and subjects will remain blinded to their initial treatment assignment for the duration of the entire study.

The statistical analysis will be described and fully documented in the SAP, which will be finalized prior to the start of the study. All statistical tests, between each risankizumab dose and placebo, will be performed at a two-sided alpha level of 0.025.

The statistical analyses will be performed using SAS (SAS Institute Inc., Cary, North Carolina, USA).

## 7.2 Definition for Analysis Populations

---

The intent-to-treat (ITT) Population, which includes all randomized subjects, will be used for all efficacy analyses. Subjects who are randomized to placebo in Period A and do not continue into Period B will be excluded from the analysis in Period B.

In order to evaluate the impact of major protocol deviations on the primary efficacy endpoint, additional sensitivity analyses may be performed on a per-protocol population, which excludes subjects with major protocol deviations that potentially affect the primary efficacy endpoint. If it is decided that this analysis should be performed, the criteria for exclusion of subjects from the per-protocol population will be fully defined in the classification plan, and the exclusion of subjects from the per-protocol population will be finalized before blind break and before the database lock for the primary analysis.

The following populations will be used for the safety analysis:

- The Safety Population in Period A (Safety\_A) is defined as all subjects who are randomized and received at least one dose of study drug in Period A.
- The Safety Population in Period B (Safety\_B) is defined as all subjects who received at least one dose of study drug in Period B.
- The all risankizumab treated (ALL\_RZB) Population is defined as subjects who received at least one dose of risankizumab in the study. This population will be used to provide a comprehensive summary of safety.

## 7.3 Statistical Analyses for Efficacy

---

Analysis of all efficacy endpoints in Period A will be conducted on the ITT Population, based on treatment as randomized for Period A. In addition, the primary efficacy endpoint will be analyzed in the per-protocol population, if defined.

Comparison of the primary endpoint will be made between each risankizumab dose and placebo using the Cochran-Mantel-Haenszel (CMH) test, adjusting for stratification factors. Non-responder imputation (NRI) will be the primary approach to handle missing values. To account for impact of COVID-19 pandemic, the NRI will be adjusted to NRI-C, Non-Responder Imputation incorporating multiple imputation to handle missing data due to COVID-19.

The overall type-I error rate will be strongly controlled using a graphical multiple testing procedure. The primary and ranked secondary endpoints will be first tested in the ranked order specified in Section 3 between each risankizumab dose and placebo, with a 2-sided significance level of 0.025. Continued testing will follow a pre-specified  $\alpha$  transfer path which includes downstream transfer along the endpoint sequence. More details of the graphical procedure will be specified in the SAP.

Details on the primary and other efficacy analyses will be provided in the SAP.

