## Sample Size Estimation

Under the study design with a 1:1:1 randomization, with the assumed Week 16 HiSCR response rate as summarized in Table 3, a total sample size of 222 subjects will provide 80% to 90% power to detect at least one risankizumab dose is different from placebo (with a 2-sided significance level of 0.025 for the test of each risankizumab dose versus placebo).

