**Table 3. Power with a 1:1:1 Randomization**

Assumed Dose Response Model	Assumed HiSCR Rate at Week 16 (%)			Power 
	Placebo (N = 74)	Risankizumab 180 mg (N = 74)	Risankizumab 360 mg (N = 74)	
Linear	26%	39.5%	53%	83.9%
EMax	26%	46.5%	53%	87.6%
EMax (with early plateau)	26%	50%	53%	90.6%

HiSCR = Hidradenitis Suppurativa Clinical Response

1. Power to detect at least one risankizumab dose is different from placebo, under a 2-sided significance level of 0.025 for each risankizumab dose.

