9.1 General Considerations

All efficacy analyses will be conducted in the ITT Population. In addition, Per-protocol analysis for primary endpoint will be performed. All statistical tests, between each risankizumab dose and placebo, will be performed at a two-sided alpha level of 0.025.

The Primary Analysis will be performed after the last ongoing subject has completed the Week 16 visit, and the data up to Week 16 have be cleaned. This will be the only and final analysis for the primary and ranked secondary endpoints. Study sites and subjects will remain blinded to their initial treatment assignment for the duration of the entire study.

For categorical endpoints, comparisons will be made between each risankizumab dosing group and placebo using the Cochran-Mantel-Haenszel (CMH) test, adjusting for the actual values of stratification factors. In case of any stratum with zero subject in either treatment group, no stratification factor will be controlled. Non-responder imputation (NRI) will be the primary approach to handle missing values. To account for the impact of COVID-19 pandemic, the NRI will be adjusted to NRI-C, Non-Responder Imputation incorporating multiple imputation to handle missing data due to COVID-19.

For continuous endpoints, comparisons will be made between each risankizumab dosing group and placebo based on the fixed term of treatment from a Mixed-effect Model

[figure not shown]
Repeat Measurement (MMRM) model including the Baseline value and observed measurements at all post-baseline visits, adjusting for the fixed effects of treatment, actual values of stratification factors, visit and treatment-by-visit interaction as covariates. The MMRM will be the primary approach to handle missing values.

For variables other than PGA Skin Pain NRS and HSSA, "Baseline" refers to the last non-missing observation on or before the date of the first administration of study drug or the date of randomization if no study drug is given. The "Baseline" of PGA Skin Pain NRS and HSSA is defined as the last non-missing weekly average score, calculated based on the daily scores from the past 7 days, on or before the date of the first administration of study drug or the date of randomization if no study drug is given. For variables where the assessment time is collected on the ePRO device, the baseline measurement must be prior to the time of the first administration of study drug.

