the following variables: ABS16, INF16 and DRA16 as the corresponding
lesion count at Week 16; and AN16 as the sum of ABS16 and INF16.
Determine the HiSCR status at Week 16. */
DATA ALL; SET COUNT FULL;
   IF 0<= AN16 <=0.5*AN BASE AND ABS16<=ABS BASE AND DRA16 <= DRA BASE
THEN HISCR 16=1;
   ELSE HISCR 16=0;
RUN:
/***************************
/*
         DATA HANDLING STEPS TO MERGE COVID-19 STATUS OMITTED
*/
/*
            PLACE TO ADD DATA HANDLING AND MERGING STEPS
/***************************
/*FOR MI, SKIP THE FOLLOWING CODE, PROCEED TO THE CODE AFTER ANALYSIS
MODEL *//*OVERRIDE MISSING VALUES NOT DUE TO COVID-19 WITH TRADITIONAL
NRI*/
DATA ALLF; SET ALL;
```

```
/*COVID19 XX='Y' IF MISSING AT WEEK XX IS DUE TO COVID-19; IF NOT,
OVERRIDE WITH TRADITIONAL NRI*/
 /*VARIABLE HISCR NRI 16: TRADITIONAL NRI DATA AT WEEK 16, WHICH COVERS
THE SPECIAL HANDLING SUCH AS THE BEFORE-AND-AFTER EXCEPTION IN THE
PARTICULAR STUDY PERIOD*/
 IF COVID19 MISS NE 'Y' THEN HISCR 16 = HISCR NRI 16;
PROC SORT DATA=ALLF; BY IMPUTATION SUBJID; RUN;
/**********
/*ANALYSIS MODEL*/
/***********
/*KEY CODE: ANALYZING EACH 'COMPLETE' DATASET*/
/**********/
/*COMPARE TREATMENT PLACEBO AND 360mg ONLY*/
DATA ALL; SET ALL;
  WHERE TRT01P NE "180mg";
RUN;
/***********
/*INDIVIDUAL-LEVEL DATA --> # OF RESPONDERS & # OF SUBJECTS, TO BE READ-
IN TO PROC STDRATE */
PROC FREQ DATA=ALL;
 BY IMPUTATION;
 TABLES TRT2*STRATA*HISCR 16/LIST NOCUM NOPRINT OUT=COUNT TABLE;
 /*TRT2 = 1 as 360mg and 0 as placebo*/
DATA COUNT TABLE; SET COUNT TABLE;
 DROP PERCENT;
PROC TRANSPOSE DATA=COUNT TABLE OUT=FREQ TABLE PREFIX=RESP;
ID HISCR 16;
BY IMPUTATION TRT2 STRATA;
VAR COUNT;
RUN:
DATA FREQ TABLE1; SET FREQ TABLE;
 CASE=RESP1;
 SIZE=SUM(RESP0, RESP1);
 KEEP IMPUTATION TRT2 STRATA CASE SIZE;
RUN;
/*CALCULATE THE COMMON RISK DIFF FOR EACH COMPLETE DATASET*/
PROC STDRATE DATA=FREQ TABLE2
 METHOD=MH STAT=RISK EFFECT=DIFF;
 BY IMPUTATION;
 POPULATION GROUP=TRT2 EVENT=CASE TOTAL=SIZE;
 STRATA STRATA / ORDER=DATA STATS(CL=NONE) EFFECT;
 ODS OUTPUT EFFECT=EFFECT;
```

```
RUN;
/*COMBINING RESULTS USING PROC MIANALYZE*/
/*************************
PROC MIANALYZE DATA=EFFECT;
   ODS OUTPUT PARAMETERESTIMATES=RISK_DIFF_MH;
   MODELEFFECTS RiskDiff;
   STDERR StdErr;
RUN;
```

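### The SAP's sample code leaves the responder count blank, not 0, for an arm-stratum without responders, and no printed step repairs it

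*Protocol*

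**What the plan says.** Protocol 7.3 analyses the primary endpoint in all randomised subjects, each dose against placebo, "using the Cochran-Mantel-Haenszel (CMH) test, adjusting for stratification factors". Protocol 5.8 defines the strata: prior anti-TNF exposure, and Hurley I, II or III among the TNF-naive. "Therefore, there will be 4 strata in total". Neither document gives their sizes.

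SAP 9.3.2 makes NRI-C the primary approach to missing data, and SAP 9.2.1 refers to Appendix E for its details. Appendix E 2.5.1 asks for a treatment difference and standard error from each completed dataset. Section 3.0 prints sample code for this:

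- PROC FREQ tabulates arm by stratum by response, within each imputation: "TABLES TRT2*STRATA*HISCR 16/LIST NOCUM NOPRINT OUT=COUNT TABLE".
- PROC TRANSPOSE turns the counts into RESP0 (non-responders) and RESP1 (responders).
- A data step writes FREQ TABLE1 with `CASE=RESP1` and `SIZE=SUM(RESP0, RESP1)`.
- PROC STDRATE then estimates the Mantel-Haenszel risk difference, reading FREQ TABLE2.

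The MI sensitivity analysis skips only the NRI override and uses the same estimation block. The one rule for sparse strata is in SAP 9.1: "In case of any stratum with zero subject in either treatment group, no stratification factor will be controlled".

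**The concern.** The TABLES statement carries no option to keep empty cells. If an arm has no responder in a stratum, there is no response = 1 row to transpose, so RESP1 is blank. SUM ignores a blank, so SIZE is still correct. A plain assignment does not, so CASE is blank. The mirror case, an arm with no non-responder, is handled correctly. The asymmetry looks like an oversight rather than a choice.

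If a record with a blank event count is excluded, its stratum is left with one arm and cannot contribute to the stratified difference. Randomised subjects would then leave the ITT comparison because of how they responded. The SAP 9.1 rule does not help, because it is triggered by no subjects rather than no responders. The table is also built separately for each of the 30 imputations, so a stratum could be blank in some and not in others. Rubin's rules would then pool estimates from different sets of subjects.

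**Working it through.** **Trace of the printed code, with illustrative counts for a stratum of 5 per arm**

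| Arm-stratum | RESP0 | RESP1 | CASE | SIZE |
|---|---|---|---|---|
| 3 of 5 respond | 2 | 3 | 3 | 5 |
| 5 of 5 respond | blank | 5 | 5 | 5 |
| 0 of 5 respond | 5 | blank | blank (should be 0) | 5 |

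**Inputs from the plan**

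- Allocation and size: "Under the study design with a 1:1:1 randomization", 222 subjects, so 74 per arm.
- Level: "with a 2-sided significance level of 0.025 for the test of each risankizumab dose versus placebo".
- Planning rates: placebo 26%, 360 mg 53%, 180 mg 39.5% (linear model).

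**The plan's own figure first.** Table 3 gives 83.9 / 87.6 / 90.6% power for at least one dose. With a shared placebo arm, a continuity-corrected test gives 84.5 / 88.0 / 91.0% and Fisher's exact test 84.8 / 88.2 / 91.1%, within 0.9 points. An uncorrected test gives 88.5 / 91.4 / 93.7%. The inputs are therefore read correctly. Table 3 does not depend on the code in question.

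**Assumptions.** Strata of 18 / m / 32 / remainder per arm with m = 2, 4 or 7; the same rates in every stratum; and a stratum with a blank in either arm is deleted.

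**How often a blank arises.** An arm-stratum of m subjects has no responder with probability (1 − p)^m. At m = 5 this is 0.74^5 = 22.2% for placebo, 0.47^5 = 2.3% for 360 mg and 0.605^5 = 8.1% for 180 mg. Placebo alone is empty in 0.222 × (1 − 0.023) = 21.7% of cases and 360 mg alone in 0.023 × (1 − 0.222) = 1.8%, a ratio of about 12. For 180 mg the pair is 20.4% and 6.3%.

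Over all strata, P(at least one blank) = 1 − Π(1 − 0.74^m)(1 − 0.47^m). For m = 2, 4 and 7 this gives 65%, 34% and 14%. At m = 4 the smallest stratum alone gives 1 − 0.700 × 0.951 = 33.4%; the other strata add the rest.

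**What deletion does.** The Mantel-Haenszel difference weights each stratum by n1·n0/(n1 + n0). With equal arms a stratum of m carries m/74 of the weight. Take m = 7 with no placebo responder and the active arm at its expected 53%:

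- kept: (7 × 53 + 67 × 27)/74 = 29.5 points
- deleted: 27.0 points, a fall of 2.5
- averaged over all trials: 2.5 × 0.14 ≈ 0.35 points

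Simulation with a Wald test at two-sided 0.025 agrees. For m = 2 to 7 the mean 360 mg difference over all trials falls by about 0.2 to 0.35 points and power by about 1.2 to 1.5 points. Power for 180 mg (linear model) falls by about 1.7 to 2.4 points.

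A second run of 400,000 trials used other stratum sizes. Its base power is slightly lower. The 360 mg results are:

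| Smallest stratum per arm | Trials with a deletion | Mean difference, kept → deleted | Power, kept → deleted |
|---|---|---|---|
| 5 | 24.5% | 27.0 → 26.6 | 88.5 → 87.1% |
| 8 | 9.8% | 27.0 → 26.7 | 88.5 → 87.4% |
| 10 | 5.6% | 27.0 → 26.8 | 88.5 → 87.7% |
| 14 | 2.3% | 27.0 → 26.9 | 88.4 → 88.0% |

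Across that run, with the smallest stratum at 1 to 10 per arm, the mean fell by 0.1 to 0.4 points for 360 mg and 0.1 to 0.2 for 180 mg. With no true effect the mean stays at 0, and the rejection rate goes from about 0.028 to 0.025–0.027.

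**Unequal stratum rates (assumed).** In two scenarios 360 mg power fell by 2.7 and 4.5 points. In a third, with no drug effect in a low-response stratum, the mean difference rose by 0.6 points.

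**The case against.** The strongest reply is that this is not the analysis program. It is labelled sample code, it omits data-handling steps, and it does not run through as printed: the NRI override is written to ALLF while the analysis reads ALL, and PROC STDRATE reads a FREQ TABLE2 that nothing creates. The governing text in SAP 9.1, 9.3.2 and Appendix E 2.5 specifies a proper stratified CMH comparison, and a missing step between the two tables could be where blanks become 0. All of this stands. It means the documents do not show that any stratum will be lost. It does not remove the point: a zero-fill is nowhere specified, and the obvious repair, pointing PROC STDRATE to FREQ TABLE1, would keep the blank.

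Deletion of a record with a blank count is also an assumption about the software that neither document states, and the stratum sizes are invented. Both objections stand. A very small stratum might even have no subject in one arm, in which case the SAP 9.1 rule takes over and the blank no longer matters.

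A reader might infer that the fault takes a large bite out of power. In trials with a blank at 7 per arm, rejection falls from about 94% to about 84%. That is a selection effect. Those trials are mostly the ones where placebo happened to have no responder, so the full estimate is already high (29.4 points against a true 27.0), and deletion brings it back to about 27. The figures over all trials are the relevant ones.

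A reader might also infer that risankizumab always loses. In affected trials deletion raises the estimate in 34%, 26% and 13% for 360 mg (2, 4 and 7 per arm), and in about 50%, 35% and 25% for 180 mg.

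**Conclusion.** The gap in the printed code is real: an arm-stratum without responders gets a blank event count beside a correct denominator, and nothing printed or written in the SAP corrects it. Whether strata would in fact drop out is not established. That depends on an unprinted step and on how the procedure treats a blank.

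If they did, the cost under equal rates is small: about 0.1 to 0.4 points in the mean difference, and about 1.2 to 1.5 points (360 mg) or 1.7 to 2.4 points (180 mg, linear model) of power. This rests on a smallest stratum of roughly 10 or fewer per arm. At 14 or more a deletion occurs in about 2% of trials. The loss falls on risankizumab on average but not in every trial, unequal stratum rates can make it larger or reverse it, and no type I error inflation was found. Minor severity. The fault lies in SAP Appendix E 3.0; Protocol 7.3 is sound and is only the commitment affected.

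**What to change.** In SAP Appendix E 3.0, add `SPARSE` to the TABLES statement or write `CASE=COALESCE(RESP1,0)`. Reconcile FREQ TABLE1 with FREQ TABLE2, printing the missing step if there is one. Add one sentence to SAP 9.1: every stratum with subjects in both arms stays in the comparison, entering as 0 of n where an arm has no responder. The cost is one option or function call and one sentence, with no change to the planned method. It should be settled before unblinding, because afterwards it would be a change to the primary analysis made with outcomes known.
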